Jordan University of Science and Technology
Form A1- Research Fund Application (E-Submission)

A

DESCRIPTION

Title: Assessment of Pulpotomy Procedure Using NeoMTA Plus in Permanent Teeth with Carious Exposure

A-I: ABSTRACT

Vital pulp therapy is recommended for teeth diagnosed with reversible pulpitis or partially inflamed pulps in which the remaining healthy tissue can be conserved and protected by a biologically active material to generate a hard tissue barrier that seals and protects the pulp from future microbial insult. The aim of this in vivo study is to clinically and radiographically assess the outcome of full pulpotomy using a calcium silicate based material (NeoMTA Plus) in permanent teeth with carious exposure.

Ethics approval will be obtained from the institutional ethics and research committee, and the patients will be informed for the possible complication and informed consent will be obtained. Seventy patients meeting the inclusion criteria will be selected for this study and they will be subsequently followed up clinically and radiographically after 3 months, 6 months, and 1 year.

A-II: PROJECT GOALS AND OBJECTIVES

The aim of this in vivo study is to clinically and radiographically assess the outcome of full pulpotomy in cariously exposed pulps using NeoMTA Plus in permanent teeth with carious exposure.

B-I: REVIEW AND ANALYSIS OF RELATED WORK

The invading microorganisms in carious lesions are the primary cause of pulpal inflammation. Clinical signs and symptoms such as the degree and characteristics of pain do not reflect the actual histological status and subsequently the healing potential of the inflamed pulp. Vital pulp therapy is recommended for teeth diagnosed with reversible pulpitis or partially inflamed pulps in which the remaining healthy tissue can be conserved to generate a hard tissue barrier that seals and protects the pulp from future microbial insult.¹

According to Seltzer and Bender,^{2,3} pulp capping should be discouraged for carious pulp exposures, since microorganisms and inflammation are invariably associated, and it was shown that it has lower success rate than in traumatic exposure.⁴ This perspective has encouraged clinicians to deliver alternative treatments, such as pulpotomy or pulpectomy, particularly in immature permanent teeth.^{5,6}

Due to better understanding of pulp physiology, caries microbiology, and the inflammatory mechanisms responsible for irreversible changes in pulp tissue, teeth with the potential for repair and continued vitality can now be more readily identified and predictably treated.⁷

It is recognized that outcomes for vital pulp therapy can vary, depending on the age of the patient, extent of bacterial contamination, and degree of pulp inflammation. Perhaps of greater importance may be the choice of pulp capping material and the quality of the permanent restoration.⁸ Appropriate case selection, through a detailed differential diagnosis using multiple tests paired with a careful radiographic interpretation is required. A study done by Aguilar & Linsuwanont concluded that vital permanent teeth with cariously exposed pulp can be treated successfully with vital pulp therapy.⁹

The dental pulp is a highly vascular and innervated loose connective tissue that has the unusual distinction of being enclosed within a rigid envelope composed of enamel, dentin, and cementum.^{10,11} These hard tissues impart mechanical support and offer protection from the oral microbiota.¹² A comparison analysis of gene expression levels reflecting the activity of biologic cell function, proliferation, differentiation, and development found them markedly higher in young pulps compared to older dental pulps. Analyses of young dental pulps indicated a greater expression level in cell and tissue differentiation, proliferation, and development of the lymphatic, hematologic, and immune systems compared to older dental pulps where the apoptosis pathway is highly expressed.¹³

Pulpotomy defined as “the removal of the coronal portion of the vital pulp as a mean of preserving the vitality of the remaining radicular portion: may be performed as emergency procedure for temporary relief of symptoms or as a therapeutic measure.”¹⁴ After complete amputation of the coronal pulp, a capping material is placed over the pulp. The introduction of new bioactive materials makes more teeth with carious exposures viable candidates for innovative pulp therapies designed to potentiate and maintain pulp survival.

Preliminary investigations with Calcium Silicate Cements have demonstrated physio-chemical and bio-inductive properties comparable to those of MTA, indicating the potential future application of these materials in vital pulp therapy.^{15,16} Some of these tricalcium-based materials include BioAggregate (Innovative Bioceramics, Vancouver, British Columbia), Biodentine (Septodont, Cambridge, Ontario, Canada), MTA-Angelus, MTA Bio, and MTA Branco (MTA-Angelus, Londrina PR, Brazil) and NeoMTA plus (Avalon Biomed, Bradenton USA).^{17,18} Other formulations include EndocemMTA (Maruchi, Wonju-si, Gangwon-do, South Korea) and Endosequence root repair material (Brasseler USA, Savannah, Georgia). Additional compounds are currently undergoing clinical investigations to establish their safety and efficacy.^{19,20}

NeoMTA Plus (Avalon Biomed Inc. Bradenton. USA), is noncytotoxic, inhibits bacterial growth, does not contain resin, washout resistant, no staining potential, and does not require special equipment for mixing or placement. Furthermore, the fine particle size powder with the special gel creates a material that has superior handling properties. The setting time is less than 10 minutes and the manufacturer recommends no waiting time before placement of the permanent filling, which is time saving and particularly important for the early achievement of coronal seal.^{21,22,23}

B-II: SIGNIFICANCE OF WORK

Until now there are no published data available on the outcome of pulpotomy procedures using NeoMTA Plus in human teeth with carious exposure, however animal studies have shown favourable response.²⁴ Therefore; the aim of this study is to explore the clinical and radiographic outcome of pulpotomy procedures using NeoMTA plus in permanent teeth with carious exposure.

C-I: METHODOLOGY

Ethics approval will be obtained from the institutional ethics and research committee. One hundred and 20 patients meeting the inclusion criteria will be selected for the study.

Inclusion Criteria :

- Permanent teeth with mature or immature apices
- Have no significant medical problems
- The tooth should give positive response to cold test and Electric Pulp Test (EPT)
- Probing pocket depth and mobility within normal limits
- No Signs of pulp necrosis including sinus tract or swelling
- Radiographically ; caries either exposing the pulps or reaching more than $\frac{2}{3}$ the distance from the dentino-enamel junction (DEJ) to the pulp
- The tooth can be restored via direct restoration

Exclusion criteria :

- Medically compromised patients
- Negative response to cold test
- Mobility
- Sinus tract
- Swelling
- Non restorable teeth or badly broken teeth

All the patients will be informed for the possible complication and informed consent will be obtained. After Clinical and radiographic examination the tooth will be anaesthetised using Lidocaine 2 % and adrenaline 1/80000 and subsequently isolated using rubber dam . Then the tooth will be wiped with a gauze soaked in 2.5% sodium hypochlorite to disinfect the surface

Cavity will be prepared using high speed fissure bur and the caries will be excavated using large

round bur in the slow speed handpiece. The exposed pulpal tissue will be amputated using sterile round bur in the high speed hand piece to the level of canal orifices (full pulpotomy). A pellet soaked with sodium hypochlorite (2.5%) will be placed for 3-5 minutes over the pulpal wound to achieve hemostasis.

NeoMTA Plus (Avalon biomed Inc, USA) will be mixed according to manufacturer instructions, then it will be placed over the pulp wound, then permanent restoration will be placed in the same visit. The patient will be reviewed after one week to evaluate symptoms.

The patients will be asked to score the preoperative pain levels using visual analogue scale from 0-10, 0 equals no pain while 10 is maximum value. The patients will be contacted by phone 2-3 days after treatment to score pain levels again.

The patients will be followed up after 3 months, 6 months, and 1 year , all teeth will be examined both clinically and radiographically to see if there is any symptoms, tenderness to percussion, presence of calcifications, resorption or new apical pathosis.

The outcome will be considered as unfavorable if one or more of the following is present: pain, tenderness to percussion, sinus tract, swelling, evidence of new periapical lesion, or persistence of a preoperative lesion. In case of failure RCT will be initiated.

C-II: LOCATION AND SAFETY CONSIDERATIONS

The clinical procedures will be done at the postgraduate clinics at the faculty of dentistry (JUST), universal precautions regarding infection control and radiation safety will be followed and respected.

C-III: EXPECTED RESULTS/OUTPUTS

To maintain the vitality of the teeth and to preserve them in function without any signs and symptoms of apical periodontitis.

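### Does an inclusion criterion that can be met without pulp exposure leave the sample and the success-rate denominator undefined?

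*Protocol*

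**What the plan says.** **Aim.** Section A-II sets out to assess "full pulpotomy in cariously exposed pulps using NeoMTA Plus in permanent teeth with carious exposure". The title, the abstract (A-I) and the significance section (B-II) describe the population in the same terms.

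**Eligibility.** Section C-I lists 7 inclusion and 6 exclusion criteria. The radiographic one offers two alternatives, "caries either exposing the pulps or reaching more than" two thirds of the distance from the dentino-enamel junction to the pulp.

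**Sample.** The abstract states "Seventy patients meeting the inclusion criteria will be selected for this study and they will be subsequently followed up clinically and radiographically". Section C-I states "One hundred and 20 patients meeting the inclusion criteria will be selected for the study". The two figures, 70 and 120, disagree; that is a separate matter and nothing here depends on it.

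**Procedure.** Section C-I continues "After Clinical and radiographic examination the tooth will be anaesthetised". Isolation, cavity preparation and caries excavation follow, and then "The exposed pulpal tissue will be amputated using sterile round bur in the high speed hand piece to the level of canal orifices". Haemostasis, placement of NeoMTA Plus and the permanent restoration complete the visit. The reviews, the definition of an unfavourable outcome and the action on failure come after that.

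**The concern.** Eligibility appears to be judged on the examination and the film, before anyone knows whether the pulp is exposed. A tooth with deep caries can qualify on the second alternative and still show no exposure once the caries is removed. Read literally, the abstract selects that tooth's patient and follows the patient up, while the procedure has no exposed tissue to act on and the aim does not cover the tooth.

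This is a single-group study whose main product is a proportion of favourable outcomes. If the stated number counts patients who passed a pre-operative screen, while the aim needs exposed pulps treated by pulpotomy, then the denominator is not tied to the population in the title. Were unexposed teeth to enter the success rate, that rate would describe a mixed population. Were they to drop out unremarked, fewer teeth would be treated than the sample statement implies.

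**Working it through.** **1. What the criteria require.** Inclusion 7 + exclusion 6 = 13 listed items. Items that refer to exposure found at excavation: 0 of 13. Alternatives in the radiographic criterion that can be met without exposure on the film: 1 of 2. The gap in the wording is therefore confirmed.

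**2. Whether the other passages close it.** Take a tooth that meets the criteria and is not exposed after excavation.

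- *Treatment.* C-I amputates exposed tissue and describes no other treatment path. The protocol nowhere indicates that a pulpotomy would be done on an unexposed pulp.
- *Follow-up.* Only the summary sentence in the abstract joins selection to follow-up. The selection sentence in C-I stops at selection. The detailed follow-up text in C-I comes after the amputation, the capping material, the restoration, a one-week review and a pain call timed from treatment. In that order, the patients and teeth reviewed at 3 months, 6 months and 1 year are most naturally those treated.
- *Outcome.* The aim is the outcome of full pulpotomy. A tooth without a pulpotomy has none.
- *Timing of the count.* C-I places the examination before anaesthesia, but does not say that selection is complete at that point.

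Read together, the film screens, excavation shows whether there is exposure, and the exposed pulp is treated and followed.

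**3. Size.** There is no figure to reproduce: neither 70 nor 120 comes with a success rate, a precision target or an allowance for losses. For illustration only, let u be the share of selected teeth found unexposed. The documents give no value; 10% to 40% is assumed.

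Treated teeth = N × (1 − u):

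- N = 70: 70 × 0.9 = 63, down to 70 × 0.6 = 42.
- N = 120: 120 × 0.9 = 108, down to 120 × 0.6 = 72.

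The 95% half-width is 1.96 × √(p(1 − p)/n), with an assumed success rate p of 80% or 90%. In percentage points:

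| N | Treated teeth (u = 0 → u = 40%) | p = 90% | p = 80% |
|---|---|---|---|
| 70 | 70 → 42 | 7.0 → 9.1 | 9.4 → 12.1 |
| 120 | 120 → 72 | 5.4 → 6.9 | 7.2 → 9.2 |

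Even at the upper end of the assumed range, the half-width widens by 1.5 to 2.7 points (6.9 − 5.4 = 1.5; 12.1 − 9.4 = 2.7). With unexposed teeth left out, this is a loss of precision only. The protocol sets no precision target against which to call it a failure.

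**The case for a change.** The strongest case for a change is that eligibility, and who counts toward the stated number, belong in the protocol and cannot be left to an analysis plan. A screen needs a later step that settles who has entered the study, and none is written. Treating the procedure's reference to exposed tissue as a silent entry rule means that fewer patients than stated may be treated and followed, which does not sit with the abstract's sentence. One added line would remove the doubt at little cost.

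Part of this stands. The text is silent on the qualifying but unexposed tooth, and the abstract, taken alone, joins selection to follow-up more tightly than the methods do. But one summary sentence does not outweigh the order of events in the methods. The added line would also mainly set a success-rate denominator and a rule for reporting patient flow. Those are commonly settled in a statistical analysis plan, which may exist but was not available here. It would record what analysts would do anyway.

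**Conclusion.** No change to the plan is needed. The radiographic criterion is a reasonable screen, wider than the target population because exposure cannot be confirmed until the caries is removed. The aim and the procedure then narrow the population to exposed pulps treated by pulpotomy. The protocol leaves a detail unwritten, and the sensible way to fill it is clear: report outcomes for the treated teeth and state how many qualified but were not exposed.

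The effect on any result cannot be sized from the document, and neither bias nor a wrong result is shown. The conclusion rests on two readings: that the follow-up text in C-I refers to treated teeth, and that pulpotomy is done only where the pulp is exposed. Both are the natural sense of the text. Evidence that unexposed teeth were pulpotomised, or were counted as successes without a pulpotomy, would reopen the point. How an unexposed tooth is managed is a clinical matter on which no view is taken here.

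### Does taking the repeat pain score by telephone spoil the comparison with a preoperative score on a visual analogue scale?

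*Protocol*

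**What the plan says.** Two consecutive sentences in section C-I (Methodology) of the protocol deal with pain scoring. Before treatment, patients "score the preoperative pain levels using visual analogue scale from 0-10, 0 equals no pain while 10 is maximum value". After treatment, "The patients will be contacted by phone 2-3 days after treatment to score pain levels again". The second sentence does not name the instrument again. Neither sentence says whether the patient marks a line, points to a number or speaks one.

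The other follow-up contacts in C-I are described differently. At one week, "The patient will be reviewed after one week to evaluate symptoms". At 3 months, 6 months and 1 year, "all teeth will be examined both clinically and radiographically to see if there is any symptoms". No 0-10 score is stated for these contacts, though none is ruled out.

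The outcome rule, also in C-I, is a list of signs: "The outcome will be considered as unfavorable if one or more of the following is present: pain, tenderness to percussion", followed by sinus tract, swelling and periapical findings. Section B-II gives the purpose: "the aim of this study is to explore the clinical and radiographic outcome of pulpotomy procedures".

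**The concern.** A visual analogue scale is ordinarily a line that the patient sees and marks. It cannot be shown on a telephone call. The protocol names the visual scale for the first score and the telephone for the second, with no printed copy and no spoken version. Read literally, the first score could be a mark on a line and the second a spoken number.

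If so, the way of scoring would coincide with the time point in every patient. No comparator arm is described, so there would be no group in which the same switch happened and against which it could be cancelled out. A before-after difference would contain both the change in pain and any shift due to the method. Neither a larger sample nor a later analysis could separate the two. How a score is collected is also settled when the data are gathered, so a statistical analysis plan could not repair it afterwards. On that reading, the early pain result would be hard to interpret.

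**Working it through.** The protocol gives no figure that rests on the pain score: no standard deviation, effect size, power or sample-size calculation uses it. There is nothing to reproduce, so the check is a reading of the passages side by side.

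**Step 1: what is fixed at each time.**

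| Item | Preoperative score | Repeat score |
|---|---|---|
| Range | 0-10 | not restated; pain is scored again |
| End points | "0 equals no pain while 10 is maximum value" | not restated |
| Instrument | visual analogue scale | not named |
| Contact | not stated | telephone, 2-3 days after treatment |
| Mark on a line or spoken number | not stated | not stated; a spoken value is implied by the call |

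No row contains a contradiction. The only tension is between the word visual in the first column and the telephone in the second.

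**Step 2: the possible readings.**

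- *A spoken 0-10 rating both times.* The term visual analogue scale is used loosely. The method of response is the same and only the name of the instrument is inexact.
- *A printed scale both times, with the patient reading a number from it.* The method of response is again the same.
- *A marked line first and a spoken number second.* The method differs, and it differs with time.

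The protocol does not state the third reading. It has to be built from the word visual together with the absence of any instruction for the call.

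**Step 3: the effect under each reading.** Write D for the true mean change in pain and m for the mean shift due to method. If the shift is assumed to be additive, then

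observed mean change = D + m.

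- First or second reading: m = 0 for the difference between marking and speaking, so observed mean change = D.
- Third reading: observed mean change = D + m, with m of unknown size and sign. The number of patients does not enter the formula, so recruiting more would not reduce m.

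The document provides no value or range for m. The additive form is itself an assumption.

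**Step 4: what uses the score.** The aim in B-II is the clinical and radiographic outcome. The favorable/unfavorable rule takes pain as present or absent alongside examination signs and sets no cut-off on the 0-10 scale. No before-after pain comparison is stated anywhere in the protocol. A non-zero m would therefore affect only a descriptive comparison that the protocol does not describe, and would leave the stated outcome as it is.

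**The case for a change.** The strongest case for acting is that the protocol names an instrument and then a means of contact by which that instrument cannot be shown. Either the method changes between the scores, or the instrument is misnamed, or there is a printed copy that the text does not mention. The first two would each justify correcting the wording. The obvious use of a preoperative and a repeat 0-10 score is to compare them, even if no such analysis is written down. No later visit has a stated score that could serve as a comparison by the same method. A sentence and a short script would cost almost nothing, and the method of scoring cannot be recovered once the data are in.

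Part of this stands. The wording is awkward, the detail belongs to data collection and not to the analysis plan, and if the methods did differ, the confusion with time would be complete.

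The rest carries less weight. The argument relies on what the text leaves out, and the text is a short research-fund application in which the absence of a call script is weak evidence that none exists. The number of later visits without a stated score has no bearing on whether the two stated scores share a method. Nor is the remedy as clean as it seems. A printed card kept for the call still produces a spoken value, so it matches the first score only if the patient reads out a number both times. A spoken scale at both times still leaves face-to-face against telephone, assuming the preoperative score is taken in the clinic. A rewording would reduce the difference without removing it.

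**Conclusion.** The concern does not call for a change to the plan. The protocol describes one 0-10 scale with both ends defined and has patients score pain again, most naturally as the same rating repeated. The gap is silence on how the number is obtained, which those running the study would ordinarily fill in a call script or case report form. If the loose use of visual analogue scale is a slip, it is one of naming.

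The size cannot be given. The shift is zero if one method of response is used at both times and unknown otherwise; the document supports no range. Whatever its value, it does not reach the favorable/unfavorable classification, which uses pain as present or absent.

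This rests on two assumptions: that the repeat score is meant as the same 0-10 rating, and that the pain scores serve only as description beside the clinical and radiographic outcome. If a before-after change in pain were made a formal outcome, and the first score proved to be a measured mark on a line, the question would need to be reopened. Nothing in the present text says either. Anyone reporting the two scores should simply say how each was obtained.

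### A new, symptom-free furcal radiolucency is scored favourable, because the only new radiographic failure sign is a periapical lesion

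*Protocol*

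**What the plan says.** All the relevant text is in the protocol, mostly in section C-I (Methodology).

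- **Failure rule, clinical signs:** "The outcome will be considered as unfavorable if one or more of the following is present: pain, tenderness to percussion, sinus tract, swelling".
- **Failure rule, radiographic signs**, continuing the same sentence: "evidence of new periapical lesion, or persistence of a preoperative lesion". The next sentence makes failure the trigger for root canal treatment.
- **Recall examination:** besides symptoms and percussion, the teeth are checked for "presence of calcifications, resorption or new apical pathosis".
- **Recall times:** "The patients will be followed up after 3 months, 6 months, and 1 year".
- **Eligible teeth:** "Permanent teeth with mature or immature apices". No criterion refers to tooth type or number of roots.
- **Procedure:** the exposed pulp is removed "to the level of canal orifices (full pulpotomy", and NeoMTA Plus is laid on the wound.

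Section C-III gives the expected result as teeth kept in function "without any signs and symptoms of apical periodontitis". The protocol defines only the unfavourable outcome, so favourable is the remainder. No furcal or inter-radicular finding is mentioned anywhere.

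**The concern.** For new disease on a film, the rule looks at one site, the root apex. In a multi-rooted tooth, a wound at the canal orifices lies at the floor of the pulp chamber, above the furcation. The bone nearest the treated site is therefore not among the places where a new lesion counts. That last step is dental reasoning and is not stated in the protocol.

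The study's purpose is to assess the outcome both clinically and radiographically, and no comparator is described. A sign left out of the failure list cannot cancel between groups. It passes straight into the single favourable proportion that the study will report, and a larger sample would not remove it.

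**Working it through.** **1. Does the rule miss the finding?** Take a multi-rooted tooth with no lesion before treatment, a new furcal radiolucency at recall, and no clinical complaint or sign. Against the six items:

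| Item in the failure rule | Met? |
|---|---|
| Pain | No |
| Percussion tenderness | No |
| Sinus tract | No |
| Swelling | No |
| New periapical lesion | No; the lesion is at the furcation |
| Preoperative lesion that persists | No; there was none before treatment |

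The tooth is favourable by remainder.

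**2. Does other text close the gap?** The recall item on new pathosis is apical, and so is the expected result in C-III. Probing depth and mobility are entry criteria, but neither is named at recall or in the failure rule. Nothing else gives this finding a route to unfavourable.

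**3. Which furcal lesions are already caught?** One that comes with any of the four clinical signs is caught. One seen before treatment that persists can be caught, because that item names no site. The gap is limited to furcal lesions that are both new and isolated.

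**4. Direction.** The rule is met by any one item. Adding an item can move a tooth only from favourable to unfavourable, so leaving it out can only raise the favourable rate.

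**5. Effect per tooth.** Two sample sizes are stated, 70 in the abstract (A-I) and 120 in C-I. That conflict is a separate matter, so both are used. Assuming one tooth per patient:

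- 1/70 = 1.4 percentage points
- 1/120 = 0.8 percentage points

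**6. Possible total.** The protocol gives neither the share of multi-rooted teeth nor the frequency of the finding. Assumed ranges are 50-80% multi-rooted, and 0-5% of those with a new isolated furcal lesion.

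Overstatement = (share multi-rooted) × (share of those with the finding)

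- Lower end: 0.50 × 0 = 0 points (the same at 0.80)
- Upper end: 0.80 × 0.05 = 0.04, or 4 points
- In teeth, the upper end is 0.04 × 70 = 2.8 of 70, or 0.04 × 120 = 4.8 of 120

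**7. Scale against sampling error.** The protocol states no expected rate, so a favourable rate near 85% is assumed for illustration. The 95% Wilson interval is 75.7-92.1% for 60/70 (half-width (92.1 − 75.7)/2 = 8.2 points) and 77.5-90.3% for 102/120 (half-width (90.3 − 77.5)/2 = 6.4 points). Even the upper end of the assumed bias is smaller than either half-width.

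**The case against.** The strongest reply is that the plan agrees with itself. The recall item, the failure sign and the expected result all concern the apex, so nothing is contradicted. Furcation, tooth type and root number are never mentioned; that a furcal lesion can occur alone and signals failure is clinical knowledge from outside the protocol. The film view is not stated either, so it is an assumption that the furcation can be read on the planned films. Nothing rules out a frequency of zero, and there is no success threshold or hypothesis test that a shift of a few points could reverse.

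Most of this stands as a limit on size and certainty. It does not remove the gap. The protocol itself fixes the list, admits multi-rooted teeth, and leaves this finding on the favourable side. Consistent wording does not help if all of it looks at the same single site. An examiner might stretch the word periapical to include the furcation, but the score would then depend on who reads the film.

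A reader might infer more than the text supports:

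- *That the radiographic signs cover periapical lesions only.* This is true only of new lesions, since the persistence item names no site.
- *That every furcal lesion is scored favourable.* Those with a listed clinical sign are not.
- *That the success rate is inflated.* It could be. Without a frequency, the documents do not show that it will be.

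A last objection concerns the remedy. The same list triggers root canal treatment, so lengthening it without comment would also widen a treatment rule. That is accepted, and the fix is restricted accordingly.

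**Conclusion.** The point holds in a limited form. As C-I is written, a new furcal radiolucency without any of the four clinical signs is scored favourable, and no other text prevents it. The possible error runs one way, upward, at 1.4 points per tooth with 70 patients or 0.8 with 120.

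The total is 0 to 4 points under the assumed ranges. Those ranges come from no source in the protocol, and the total could be nil. The conclusion also assumes one tooth per patient, that multi-rooted teeth are in fact enrolled, that the furcation is readable on the films, and that a new furcal radiolucency is a sign of disease. The change is worth making because the defect is in the outcome definition itself and costs little to correct before scoring begins.

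**What to change.** In C-I, for outcome scoring only:

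- Read the preoperative film and every recall film for both periapical and furcal (inter-radicular) radiolucency, and record any that is new since the preoperative film.
- Count either one as an unfavourable radiographic outcome in the analysis.

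The sentence after the failure list ties failure to root canal treatment. The sponsor must therefore reconcile the scoring definition with that trigger and state how the two relate. No clinical rule is proposed here.

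The cost is a few words in C-I and one more item on the film-reading form, with no added visit and, if the planned view shows the furcation, no added film. The downside is that the reported favourable rate may be slightly lower.

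### Could the undated outcome rule score a healing preoperative lesion as a failure and lose its 1-year result?

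*Protocol*

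**What the plan says.** All of this stands in the protocol, section C-I (Methodology), unless noted.

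- **Visits.** "The patients will be followed up after 3 months, 6 months, and 1 year", each with a clinical and a radiographic examination.
- **What the examination looks for.** "to see if there is any symptoms, tenderness to percussion, presence of calcifications, resorption or new apical pathosis".
- **Outcome rule and consequence.** "The outcome will be considered as unfavorable if one or more of the following is present: pain, tenderness to percussion, sinus tract, swelling", and the list closes, followed by its consequence, with "evidence of new periapical lesion, or persistence of a preoperative lesion. In case of failure RCT will be initiated". No visit is attached to the rule or to the RCT sentence, and persistence is not defined. Failure has no definition apart from the unfavourable rule.
- **Eligibility.** "The tooth should give positive response to cold test and Electric Pulp Test (EPT"), and there must be no signs of necrosis such as a sinus tract or swelling. The radiographic criterion concerns caries depth. Neither list excludes a tooth with a periapical lesion.
- **Sample size.** The abstract (A-I) has "Seventy patients meeting the inclusion criteria will be selected for this study"; C-I has "One hundred and 20 patients meeting the inclusion criteria will be selected for the study". That difference is a separate matter. Both figures are used below.

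**The concern.** Most items in the outcome rule are adverse whenever they appear. Persistence is different, because it has meaning only relative to the time allowed for a lesion to resolve, and no time is given. The rule follows directly after the three visits, so it can be read as applying at each of them. On that reading a lesion that is smaller but still visible at 3 or 6 months is unfavourable, and the tooth goes to RCT.

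Three things would then be at stake:

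- Two examiners could classify the same healing tooth differently.
- If the aim is the state at 1 year, the error runs one way only: success is understated among teeth that began with a lesion.
- The loss is permanent, because no later analysis can show what the pulpotomy alone would have achieved at 1 year once RCT has been done.

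The list of follow-up findings seems to add to this. It mentions new apical disease but not the state of a lesion already present, on which the outcome rule depends.

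**Working it through.** The protocol states no expected success rate, power or precision, so there is no figure of its own to reproduce. The check has two parts: which teeth the ambiguity touches, and how many it would take to matter.

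**Which teeth**

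| Tooth | Rule applied at every visit, any visible lesion counts | Rule applied at 1 year, any visible lesion counts |
|---|---|---|
| No preoperative lesion | not affected | not affected |
| Lesion gone by 3 months | favourable on this item | favourable on this item |
| Lesion still visible at 1 year | unfavourable | unfavourable |
| Lesion visible at 3 or 6 months, gone by 1 year | unfavourable | favourable on this item |

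Between these two readings only the last row changes. A third reading, in which persistence means no reduction in size, would also spare a lesion that is shrinking at 1 year. On every reading the affected teeth are a subset of those with a preoperative lesion.

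**How many would matter**

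Inputs: n = 70 (A-I) or n = 120 (C-I), taking one tooth per patient. True success p = 0.80, 0.90 or 0.95 is an assumption.

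- Shift per tooth = 100/n: 100/70 = 1.43 points; 100/120 = 0.83 points.
- 95% half-width = 196 × √(p(1−p)/n), in points. For example, with p = 0.90 and n = 70: 196 × √(0.09/70) = 7.03.
- Teeth needed to equal the half-width = half-width ÷ shift per tooth, rounded up.

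| p | n = 70: half-width | teeth | n = 120: half-width | teeth |
|---|---|---|---|---|
| 0.80 | 9.37 | 6.56 → 7 | 7.16 | 8.59 → 9 |
| 0.90 | 7.03 | 4.92 → 5 | 5.37 | 6.44 → 7 |
| 0.95 | 5.11 | 3.57 → 4 | 3.90 | 4.68 → 5 |

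As shares of all teeth, this is 4/70 = 5.7% to 7/70 = 10%, or 5/120 = 4.2% to 9/120 = 7.5%.

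**Range of the shift**

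Let L be the share of teeth with a preoperative lesion and g the share of those that are visible at an interim visit but gone by 1 year. The shift in points is 100 × L × g. Both inputs are assumptions, since the document gives neither.

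- Low end, L = 5%, g = 25%: 1.25 points, which is 70 × 0.0125 = 0.9 tooth or 120 × 0.0125 = 1.5 teeth.
- Middle, L = 10%, g = 50%: 5 points, which is 3.5 or 6 teeth.
- High end, L = 20%, g = 50%: 10 points, which is 7 or 12 teeth.

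At p = 0.90 the middle case lies below the sampling error at either size (7.03 and 5.37 points) and the high case lies above it. The high case needs one tooth in five to enter with a lesion and half of those lesions to clear late. The document supports neither figure, and the cold-test, EPT and necrosis criteria may keep L small.

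**The follow-up list**

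The list of examination findings also leaves out sinus tract and swelling, which the outcome rule names. It is therefore a summary and not a complete specification. Radiographs are taken before treatment and at all three visits, so the images needed to judge a preoperative lesion will exist.

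**The case for a change.** The strongest case for changing the text is that RCT acts on the tooth during follow-up. An analysis plan can name the visit at which success is counted, but it cannot restore a pulpotomy result that was ended at 3 months. The outcome rule and its link to RCT stand in the protocol, and the rule itself presupposes that some enrolled teeth have a lesion.

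Much of this stands: the rule names no visit, persistence is undefined, such teeth are eligible, and the loss could not be undone. Three things weaken it.

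- The 1-year result is lost only in a limited sense. A tooth scored unfavourable early stays in the analysis as a failure and does not become missing.
- Counting failure at any visit is a legitimate, conservative composite. It agrees with C-III (Expected Results), which looks for teeth free of apical periodontitis. The harm arises only if 1-year success is the target, and the protocol never says that it is.
- The obvious remedy, judging persistence at 1 year, does not reach the irreversible part. It helps only if a tooth with a visible lesion is not sent to RCT beforehand. That is a clinical rule, and a statistical review should not set it.

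**Conclusion.** No change to the plan follows. The protocol leaves unwritten the visit at which persistence is judged and whether a shrinking lesion counts. It does not contradict itself on the point, and a sensible reading is available, so this is missing detail that investigators and analysts would be expected to settle when they apply the rule.

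The size cannot be derived from the document. Per tooth it is 1.4 points (n = 70) or 0.8 points (n = 120). It stays below the 95% sampling error unless at least 4 to 7 teeth of 70, or 5 to 9 of 120, are affected. These thresholds assume true success of 80-95% and one tooth per patient. They are break-even counts, not estimates of what will happen.

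If some teeth do receive RCT before 1 year solely because an old lesion is still visible, their number can be reported and the success rate recalculated with them counted as favourable. That bounds the effect with data that the trial collects anyway.
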